## 14 Appendix 2: Liver event and laboratory trigger definitions and follow-up requirements

Table 14-1 Liver event and laboratory trigger definitions

	, 55
	Definition/ threshold
LIVER LABORATORY TRIGGERS	• 3 x ULN < ALT / AST ≤ 5 x ULN
	• 1.5 x ULN < TBL ≤ 2 x ULN
LIVER EVENTS	ALT or AST > 5 × ULN
	
 
ALP > 2 × ULN (in the absence of known bone pathology)
 

	• TBL > 2 × ULN (in the absence of known Gilbert syndrome)
	
 
ALT or AST > 3 × ULN and INR > 1.5
 

	
 
Potential Hy's Law cases (defined as ALT or AST > 3 × ULN and TBL > 2 × ULN [mainly conjugated fraction] without notable increase in ALP to > 2 × ULN)
 

	Any clinical event of jaundice (or equivalent term)
	
 
ALT or AST > 3 × ULN accompanied by (general) malaise, fatigue, abdominal pain, nausea, or vomiting, or rash with eosinophilia
 

	Any adverse event potentially indicative of a liver toxicity*

\*These events cover the following: hepatic failure, fibrosis and cirrhosis, and other liver damage-related conditions; the non-infectious hepatitis; the benign, malignant and unspecified liver neoplasms TBL: total bilirubin; ULN: upper limit of normal

Table 14-2 Follow up requirements for liver events and laboratory triggers

Criteria	Actions required	Follow-up monitoring
Potential Hy's Law case a	
 
Discontinue the study treatment immediately
 
	ALT, AST, TBL, Alb, PT/INR, ALP and γGT until resolution c (frequency at
	
 
Hospitalize, if clinically appropriate
 
	Investigator discretion)
	
 
Establish causality
 
	
	Complete liver CRF	
ALT or AST		
> 8 × ULN	
 
Discontinue the study treatment immediately
 
	ALT, AST, TBL, Alb, PT/INR, ALP and γGT until resolution c (frequency at
	
 
Hospitalize if clinically appropriate
 
	Investigator discretion)
	
 
Establish causality
 
	
	
 
Complete liver CRF
 
	
> 3 × ULN and INR > 1.5	
 
Discontinue the study treatment immediately
 
	ALT, AST, TBL, Alb, PT/INR, ALP and yGT until resolution c (frequency at
	
 
Hospitalize, if clinically appropriate
 
	Investigator discretion)
	Establish causality	
	Complete liver CRF	
> 5 to ≤ 8 × ULN	Repeat LFT within 48 hours	ALT, AST, TBL, Alb, PT/INR, ALP and
	
 
If elevation persists, continue follow-up monitoring
 
	γGT until resolution c (frequency at Investigator discretion)
	
 
If elevation persists for more than 2 weeks, discontinue the study drug
 
	
	
 
Establish causality
 
	
	Complete liver CRF	

Criteria	Actions required	Follow-up monitoring
> 3 × ULN accompanied by symptoms b	
 
Discontinue the study treatment immediately
 
Hospitalize if clinically appropriate
 
Establish causality
 
Complete liver CRF
 
	ALT, AST, TBL, Alb, PT/INR, ALP and yGT until resolution c (frequency at Investigator discretion)
> 3 to ≤ 5 × ULN (patient is asymptomatic)	
 
Repeat LFT within the next week
 
If elevation is confirmed, initiate close observation of the patient
 
	Investigator discretion  Monitor LFT within 1 to 4 weeks
ALP (isolated)		
> 2 × ULN (in the absence of known bone pathology)	

Repeat LFT within 48 hours

If elevation persists, establish causality

Complete liver CRF

	Investigator discretion  Monitor LFT within 1 to 4 weeks or at next visit
TBL (isolated)		
> 2 × ULN (in the absence of known Gilbert syndrome)	
 
Repeat LFT within 48 hours
 
If elevation persists, discontinue the study drug immediately
 
Hospitalize if clinically appropriate
 
Establish causality
 
Complete liver CRF
 
	ALT, AST, TBL, Alb, PT/INR, ALP and γGT until resolution c (frequency at Investigator discretion) Test for hemolysis (e.g. reticulocytes, haptoglobin, unconjugated [indirect] bilirubin)
> 1.5 to ≤ 2 × ULN (patient is asymptomatic)	
 
Repeat LFT within the next week
 
If elevation is confirmed, initiate close observation of the patient
 
	Investigator discretion  Monitor LFT within 1 to 4 weeks or at next visit
Jaundice	
 
Discontinue the study treatment immediately
 
Hospitalize the patient
 
Establish causality
 
Complete liver CRF
 
	ALT, AST, TBL, Alb, PT/INR, ALP and γGT until resolution c (frequency at Investigator discretion)
Any AE potentially indicative of a liver toxicity*	
 
Consider study treatment interruption or discontinuation
 
Hospitalization if clinically appropriate
 
Establish causality
 
Complete liver CRF
 
	Investigator discretion

<sup>aElevated ALT/AST > 3 × ULN and TBL > 2 × ULN but without notable increase in ALP to > 2 × ULN b(General) malaise, fatigue, abdominal pain, nausea, or vomiting, or rash with eosinophilia cResolution is defined as an outcome of one of the following: (1) return to baseline values, (2) stable values at three subsequent monitoring visits at least 2 weeks apart, (3) remain at elevated level after a maximum of 6 months, (4) liver transplantation, and (5) death.

## 15 Appendix 3: Specific renal alert criteria and actions

Table 15-1 Specific renal alert criteria and actions

Serum event	
Estimated GFR* decrease ≥ 25% compared to baseline AND eGFR	Confirm ≥ 25% decrease AND eGFR* < 90 mL/min/1.73m² after 24-48 hours (h).
< 90 mL/min/1.73m 	If it persists follow up with repeat, if possible, within 2-5 days.
	Then do some frequent monitoring (preferably weekly) until event resolves or stabilizes.
	If event does not resolve or stabilize consider consulting nephrologist and/or drug interruption.
Acute Kidney Injury: Serum estimated GFR*	Follow up within 24-48h if possible.
decrease ≥ 50 % compared to baseline	If value persists, consider consulting nephrologis and/or drug interruption.
Urine event	Confirm by urinary protein creatinine ratio.  If it persists, consider consulting nephrologist and/or drug interruption.
New dipstick proteinuria ≥ 1+	Confirm value after 24-48 h, if possible.  If dipstick value confirmed:
	
 
a) perform urinary protein creatinine ratio (PCR) within 2-5 days, if possible. If PCR > 0.2 then:
 
b) perform urine microscopy and evaluate.
 
If PCR > 0.2 and /or urine microscopy has findings (e.g. crystals, casts, dysmorphic RBC, leukocytes), consider consulting nephrologist or drug interruption or discontinuation
 

New dipstick glucosuria ≥ 1+ not due to diabetes	Confirm value after 24-48 h, if possible. If it persists:
	a) perform, blood glucose (fasting)
	
 
b) perform urinary protein/creatinine ratio.
 
If PCR ratio > 0.2 and blood glucose abnormal consider consulting nephrologist and /or drug interruption or discontinuation
 

New dipstick hematuria ≥ 1+ not due to trauma	Confirm value after 24-48 h, if possible. If it persists:
	a) perform urinary protein creatinine ratio (PCR) within 2-5 days on a first morning urine collection
	b) perform urine microscopy and evaluate.
	If PCR > 0.2 and /or urine microscopy has findings (e.g. crystals, casts, dysmorphic RBC, leukocytes) consider consulting nephrologist or drug interruption or discontinuation

\* eGFR is calculated using a modified Schwartz formula

Urine samples for testing for renal monitoring, and particularly those for the PCR ratio determination, must be collected at the first morning void.

Document contributing factors in the CRF: co-medication, other co-morbid conditions, and additional diagnostic procedures performed.

Monitor patient regularly (frequency at investigator's discretion) until either:

Event resolution: estimated GFR within 20% of baseline and > 90 mL/min/1.73m^2 or PCR < 0.2;

Event stabilization: estimated GFR within 20% of baseline OR > 90 mL/min/1.73m^2 or PCR < 0.3.

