# Part 2 (Efficacy) - Overview

All participating countries and centers will be eligible for Part 2 (Efficacy).

Part 2 is a double-blind, randomized treatment epoch. Patients will receive either LCZ696 or enalapril, and matching placebo for enalapril or LCZ696, respectively. The target dose of LCZ696 for Groups 1 and 2 is dose level 4 and for Group 3 is dose level 4x, and was selected based on the Part 1 PK/PD results. Blinded study drug will be titrated to the target dose as tolerated per the safety monitoring criteria (Table 3-3) (e.g. if the patient does not experience adverse events that include symptomatic hypotension, worsening renal function, or hyperkalemia). AEs or conditions that preclude initiation or up-titration of study drug can include abnormalities in laboratory chemistry values based on local laboratory normal reference ranges and the Investigator's judgment. Additional safety monitoring will be required for Group 3 patients. Starting with the first dose of study medication, vital signs must be checked for up to 4 hours after the initial dose at each dose level (i.e. dose levels 1x through 4x, as applicable). Note: this does not apply for up-titrations following study drug interruptions or down-titrations up to the prior achieved maximal dose level). See Appendix 13 for details.

Table 3-3 Safety monitoring criteria for initiation/up-titration of study drug

	 
Parameter	Description
Potassium level	K ≤ 5.4 mmol/L (mEq/L)
Kidney function	eGFR (calculated using the modified Schwartz formula) ≥ 30% mean GFR for age (Appendix 10, Table 22-1)
Kidney function  Blood pressure	eGFR reduction < 35% compared to randomization Visit 401 (Part 2). SBP > than the calculated 5th percentile SBP for
AEs or conditions	age as described in Appendix 4  No conditions that preclude continuation
	according to Investigator's judgment, including hypotension.

## Part 2 (Efficacy) - Pre-randomization/screening epoch, Visit 301

All patients will be consented for Part 2 efficacy (parent/legal guardian ICF and if applicable, patient assent) before any study-specific procedures are performed. All patients entering Part 2 must fulfill all inclusion criteria and none of the exclusion criteria at Visit 301 (Part 2 Efficacy-Pre-Randomization/Screening). Local laboratory evaluations are required to assess the patient's eligibility at Visit 301 (refer to Table 6-1, Table 6-2 and Section 6.5.4).

Patients may enter Part 2 (Efficacy) via two pathways:

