#### 1. Serum event:

• Confirmed (after ≥ 24h) decrease in estimated glomerular filtration rate (eGFR) of ≥ 25% compared to baseline during normal hydration status as estimated by Schwartz equation AND eGFR <90 mL/min/1.73m^2

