#### 2 Urine event:

- New onset ( $\geq 1+$ ) proteinuria, hematuria or glucosuria
- New onset of proteinuria should be confirmed by urinary protein creatinine ratio

Every renal laboratory trigger or renal event as defined in Table 15-1 in Appendix 3 should be followed up by the Investigator or designated personnel.

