#### 1. Surveillance situation

If, at any time after randomization, eGFR%\* decreases by  $\geq 50\%$  from baseline (Visit 301 for Part 2), the Investigator will check for potentially reversible causes of renal dysfunction such as:

- non-steroidal anti-inflammatory drug intake, antibiotics, or other treatments known to cause creatininemia
- volume decrease, including that resulting from excessive dosing of diuretics
- urinary infection
- urinary tract obstruction
- study medication.

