#### 2. Action situation

If a patient eGFR\* decreases by  $\geq 50\%$  from baseline (Visit 301 for Part 2) (or if serum creatinine concentration rises above 3 mg/dL (265 µmol/L), the Investigator will check for potentially reversible causes of renal dysfunction (see above). If the Investigator judges that study medication has to be stopped, he/she will have to contact the Novartis medical monitor or his/her designee. Thereafter, serum creatinine assessments will have to be repeated at least each week until levels return to acceptable values. If study medication was stopped, every effort will conditions. he done to restart it again, according to clinical

\*eGFR is calculated using a modified Schwartz formula

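### Appendix 3 can class an acute kidney injury alert as stabilized on eGFR above 90 alone when baseline eGFR exceeds 180

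*Protocol*

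**What the plan says.** Protocol Appendix 3, Table 15-1, has two serum rows (eGFR in mL/min/1.73 m² throughout).

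- **25% event.** A fall of at least 25% together with eGFR below 90. Section 7.5 gives the same pairing: "compared to baseline during normal hydration status as estimated by Schwartz equation AND eGFR <90". The actions are confirmation after 24–48 hours, a repeat at 2–5 days where possible, then frequent (preferably weekly) monitoring until the event has resolved or stabilized.
- **50% event.** The row headed "Acute Kidney Injury: Serum estimated GFR" needs a fall of at least 50% and has no absolute limit. Its action is "Follow up within 24-48h if possible". If the value persists, the investigator is to consider a nephrologist and/or interrupting drug.

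One stop rule follows the whole table. Monitoring continues, at a frequency the investigator chooses, until one of two states is reached. Resolution is eGFR within 20% of baseline and above 90, or a urinary protein creatinine ratio (PCR) below 0.2. Stabilization is "Event stabilization: estimated GFR within 20% of baseline OR > 90", or a PCR below 0.3.

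Section 7.5 adds: "Every renal laboratory trigger or renal event as defined in Table 15-1 in Appendix 3 should be followed up by the Investigator". Section 15.1 also acts at a fall of 50% or more: "the Investigator will check for potentially reversible causes of renal dysfunction such as" a list that includes study medication. Its action situation then deals with stopping study drug, and continues that "serum creatinine assessments will have to be repeated at least each week until levels return to acceptable values".

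**The concern.** The alert is relative to the child's own baseline, but one limb of the stop rule is absolute. In a child with a very high baseline, eGFR can halve and still lie above 90. Appendix 3 would then call the event stabilized although nothing has recovered. The rest of the plan points the other way: the 50% row escalates if the value persists, and Section 15.1 asks for investigation and, on one reading, weekly creatinine until values are acceptable. An investigator following the stop rule could end renal-event monitoring that those two places would continue. What is at stake is consistent safety follow-up of a few children, not the efficacy result.

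**Working it through.** **Conditions.** Let B be baseline eGFR and f the fractional fall, so current eGFR is B(1 − f). The same B is assumed for alert and stop rule.

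- Alert (Table 15-1, 50% row): f ≥ 0.50.
- Stabilization (stop rule): f ≤ 0.20, or B(1 − f) > 90.

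A fall of 50% or more can never be within 20% of baseline, so only the second limb can apply. It gives f < 1 − 90/B. Together with f ≥ 0.50 this needs 1 − 90/B > 0.50, so B > 180.

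| Baseline B | 1 − 90/B | Falls meeting both rules |
|---|---|---|
| 180 or less | at most 50.0% | none |
| 190 | 52.6% | 50% to < 52.6% |
| 200 | 55.0% | 50% to < 55.0% |
| 220 | 59.1% | 50% to < 59.1% |
| 250 | 64.0% | 50% to < 64.0% |

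A grid search over eGFR in steps of 0.01, for baselines from 100 to 260, gave the same boundary. No fall of 50% or more meets the resolution rule by eGFR.

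**Example.** 200 to 95 is a fall of (200 − 95)/200 = 52.5%, so the alert fires. Since 95 > 90, stabilization is met. If the word until is taken to mean later samples only, an unchanged recheck of 95 still meets it.

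**Cover from the 25% event.** It needs eGFR below 90, so it is off throughout the overlap. When B is below 180, a 50% fall always takes eGFR below 90 and the numerical criteria of the 25% event are met too. Apart from an eGFR of exactly 90, then, the alerts that only the 50% row can catch are the ones the stop rule counts as stabilized. The ordering is also odd: 115 to 85 is a smaller fall, (115 − 85)/115 = 26.1%, yet it draws the repeat at 2–5 days and preferably weekly monitoring.

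**Who could be affected.** Table 22-1 gives 30% of mean GFR by age. From 19 months the implied mean is 38/0.30 = 126.7, so 180 is 1.42 times the mean. At 12 to < 19 months it is 31/0.30 = 103.3, a ratio of 1.74. At 6 to < 12 months it is 23/0.30 = 76.7, a ratio of 2.35. By the formula in Section 6.5.4.3, B > 180 needs creatinine below 0.413 × height/180. At assumed heights of 65, 100 and 150 cm (not in the documents) that is 0.149, 0.229 and 0.344 mg/dL. The SAP lists a separate renal table for baseline eGFR above 170, so high baselines were foreseen, but no count above 180 is given.

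**What else catches the example child.**

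- Up-titration: Table 3-3 requires a reduction of less than 35% from Visit 401, and 52.5% fails. Section 5.5.5 allows down-titration on the same criteria.
- Notable creatinine (Table 13-1, rise above 50%): at unchanged height creatinine rises by 200/95 − 1 = 111%.
- Adverse-event follow-up (Section 7.1) runs to resolution or until the event is judged permanent.
- Scheduled creatinine (Table 6-2) falls at weeks 4, 8, 12, 24, 36, 48 and 52, with gaps of 4, 4, 12, 12, 12 and 4 weeks.

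**The case against.** The best defense reads the stop rule by purpose. The PCR limbs are naturally assigned to urine events, because only those rows use PCR. By the same logic the above-90 limb belongs to the 25% event, the only row that uses 90 and the only one whose action refers to stabilization. That reading is reasonable, but it is not written. The rule stands once after the whole table without exemption, and on the purposive reading the above-90 limb simply has to be confined to the 25% event in words.

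The second argument is that the stop rule switches nothing off in the 50% row, whose recheck and escalation depend on persistence. This stands and limits the consequence. A reader might infer that a child with a halved eGFR would get no repeat value. The documents do not support that: the row asks for a recheck within 24–48 hours where possible, an unchanged 95 is a persisting value, and Sections 7.1, 7.5 and 15.1 continue regardless.

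A reader might also infer that weekly creatinine is required only once study drug is stopped. The text does not settle this. The weekly sentence follows the stop-drug step, but the next sentence opens its own condition about stopped medication, so the weekly checks can be read as covering every fall of 50% or more.

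Finally, the group is uncounted and needs both an unusual baseline and a fall in a limited band. That also stands.

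**Conclusion.** The inconsistency is real and minor. On the written text, the alert and the stabilization rule coincide exactly when B > 180 and 50% ≤ f < 1 − 90/B. This rests on the stop rule applying to every serum row and on the PCR limbs applying to urine events only.

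The documents do not support reading it as a gap that leaves children unmonitored, or as affecting many patients. Nor does it bear on the trial's result: the primary analysis, power and type I error are unaffected. Its reach in this version is very small, because recruitment closed in January 2021 and all study drug had to stop by 31 October 2021 (Amendment 7 rationale). It still merits correction, because a safety rule should not label a halved eGFR as stabilized while neighboring text asks for further action.

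**What to change.** 1. For the 50% event, limit stabilization to eGFR within 20% of the child's own baseline (160 or more when B = 200), or stable values at three consecutive checks at least 2 weeks apart. The liver appendix (Appendix 2) already uses that spacing in its definition of resolution. The second route still allows stabilization without recovery, but only after two intervals of at least 2 weeks, so at least 4 weeks of documented non-progression. The medical team should state the tolerance that counts as stable.
2. In Section 15.1, state that weekly creatinine applies to any fall of 50% or more, whether or not study drug is stopped.
3. Keep the above-90 limb for the 25% event only, where it reverses that event's own below-90 condition.

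The cost is a wording change and a few extra creatinine draws in high-baseline children with this alert. These must stay within the Appendix 6 limits of 2.5% of blood volume per session and 5% per 4 weeks. With dosing over, the main uses are checking how past alerts in children with baseline above 180 were followed up, and correcting the text before the appendix is reused.

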#### 15.1 Guidelines for the management of renal dysfunction

#### General principles:

Glomerular filtration rate in HF patients depends on intrinsic renal function and on a balance between afferent and efferent glomerular arterial tonicity. This tonicity is partly regulated by a stimulation of angiotensin II and could be affected by either study medication. Moreover, renal dysfunction may develop or may deteriorate in some patients after study drug administration. These recommendations have been developed to guide the Investigators in managing patients with renal dysfunction after randomization.

Two types of response to serum creatinine increase are described:

#### 1. Surveillance situation

If, at any time after randomization, eGFR%\* decreases by  $\geq 50\%$  from baseline (Visit 301 for Part 2), the Investigator will check for potentially reversible causes of renal dysfunction such as:

- non-steroidal anti-inflammatory drug intake, antibiotics, or other treatments known to cause creatininemia
- volume decrease, including that resulting from excessive dosing of diuretics
- urinary infection
- urinary tract obstruction
- study medication.

#### 2. Action situation

If a patient eGFR\* decreases by  $\geq 50\%$  from baseline (Visit 301 for Part 2) (or if serum creatinine concentration rises above 3 mg/dL (265 µmol/L), the Investigator will check for potentially reversible causes of renal dysfunction (see above). If the Investigator judges that study medication has to be stopped, he/she will have to contact the Novartis medical monitor or his/her designee. Thereafter, serum creatinine assessments will have to be repeated at least each week until levels return to acceptable values. If study medication was stopped, every effort will conditions. he done to restart it again, according to clinical

\*eGFR is calculated using a modified Schwartz formula

## 16 Appendix 4: American heart association (AHA) pediatric advanced life support (PALS) guidelines

Table 16-1 5th percentile systolic blood pressure table

Age	SBP percentile	SBP (mmHg)	
1 month to < 1 year	5 th	70	
1 year	5 th	72	
2 years	5 th	74	
3 years	5 th	76	
4 years	5 th	78	
5 years	5 th	80	
6 years	5 th	82	
7 years	5 th	84	
8 years	5 th	86	
9 years	5 th	88	
10 years	5 th	90	
11 years	5 th	90	
12 years	5 th	90	
13 years	5 th	90	
14 years	5 th	90	
15 years	5 th	90	

16 years	5 th	90
17 years	5 th	90

\* AHA PALS guidelines 2010 (Kleinman 2010) are widely used criteria for hypotension in acute HF patients. The formula (for 1 year and older: 70 mmHg + 2 x Age, up to age 10) is understood to provide the 5th BP percentile up to 10 years. For children 1 month to < 1 year and >10 years, the AHA PALS guidelines 2010 5th percentile is set at 70 mmHg and 90 mmHg respectively. NOTE: This formula approximates the population-based 5th percentile BP data; however, the margin of error increases with increasing age, with the PALS formula value generally providing a lower value.

#### 16.1 Guidelines for the management of blood pressure

- 1. Investigator should monitor blood pressure closely.
- 2. If symptomatic hypotension occurs:
  - Correct any treatable cause, e.g. hypovolemia
  - If hypotension persists, any antihypertensive drug and non-disease-modifying drugs, such as diuretics, calcium channel blockers (CCBs), nitrates, and α-blockers, should be down-titrated or stopped first before down-titration of the study drug is considered
  - If hypotension persists, the study drug should be down-titrated or even temporarily withdrawn. The dose re-challenge and medications adjust guidelines described in Section 5.5.5 should be adhered to as much as possible.

# 17 Appendix 5: Treatment guidelines for elevated potassium and hyperkalemia (serum potassium greater than or equal to 5.3 mmol/L)

#### General principles

Elevation of potassium levels on a non-hemolyzed specimen above the predefined values should be repeated and confirmed before any action if appropriate based on Investigator's medical judgment.

For assessment of potassium, no blood sample should be drawn by finger or heel stick. Also note that pH can affect potassium values, and that abnormal potassium values should include assessment of pH. Each 0.1 increase in pH represents a 0.6 mEq/L change in the opposite direction of the pH change.

Patients with elevated potassium value will be managed according to the corrective actions outlined below. Hyperkalemia should be followed until resolution.

